	
children with CHD based on our institutional experience and on data from the literature; there remains diminished blood-tissue contrast during the high-resolution cardiac-gated MRI. Furthermore, there have been safety concerns regarding gadolinium deposition in brain tissues after repeated GBCA exposure as well as concerns of nephrogenic systemic fibrosis (NSF) associated with GBCA injection in young children < 2 years old who may have immature renal function. The long-term health consequences of these effects in the pediatric population are unclear. For the above reasons, we seek to study the diagnostic imaging effectiveness of Feraheme (Feraheme®), an FDA-approved drug for parenteral iron supplementation, as an MRI contrast agent in children with CHD. Although Feraheme® has been approved for the treatment of iron deficiency anemia secondary to renal disease, Feraheme® has been used as an off-label MRI contrast agent at select medical centers, including a Stanford study of Feraheme®-enhanced pediatric tumor imaging under a separate IND.

STUDY DESIGN	
The study has two parts:
 
Part I: Open-label, exploratory, case-control, single-center diagnostic efficacy study in 80 children (age newborn-6 years old) to compare Feraheme®-enhanced and Ablavar®-enhanced MRI
 
Part II: Open-label, exploratory, single-center diagnostic efficacy study in 40 children (age newborn-6 years old) to validate advanced MRI techniques to enable respiratory-motion self-gated image acquisitions. Such acquisition strategies may ultimately enable high-resolution 4D MRI of children with CHD who undergo MRI during free-breathing without sedation or anesthesia.

NUMBER OF SUBJECTS	
Part I: 80 (40 control and 40 test group)
 
Part II: 40

SUBJECT SELECTION CRITERIA	
Inclusion Criteria:
 
 1. Male or female pediatric patients of all ethnicities (age newborn to 6 years) with known or suspected CHD with inconclusive echocardiographic exams and are referred for cardiovascular MRI for further evaluation of cardiac anatomy and function. 2. Written informed consent obtained from subject's legal representative/guardian(s) and ability for subject to comply with the requirements of the study.

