Zou et al. (33) in their review of 370 biopsy confirmed cases of NSF, suggest that eliminating risk factors may substantially reduce the risk of NSF without having to shift to other imaging modalities, which may incur risk of radiation and iodinated contrast-induced nephropathy. These preventable risk factors include using the lowest dose possible for diagnostic result (limiting GBCA dosage to $<0.1\text{mmol/kg}$), avoiding non-ionic linear GBCAs in those on dialysis or having $\text{eGFR} < 30\text{mL/min/1.73m}^2$, dialyzing dialysis-dependent patients promptly after exposure, and delaying GBCA administration in the setting of acute renal failure particularly when proinflammatory conditions may exacerbate oxidative stress. The Contrast Media Safety Committee of the ESUR (29) also recently published recommendations for NSF-risk mitigation where they outlined the level of evidence and identified classes of recommendations for clinical practice. For the pediatric population, no specific evidence based-guidelines exist. Guidelines for adults are typically used. There have been 10 biopsy-proven pediatric cases of NSF, but since the implementation of guidelines, no new cases in children have been reported (38). To date, no cases of NSF have been reported in very young children (38). However, it is known that children younger than 2 years have immature renal function (39). The glomerular filtration rate (GFR) of pre-term and term newborns can be as low as 40 ml/min/1.73m^2 , and it gradually increases to 66 ml/min/1.73m^2 at 2 weeks after birth (39). Due to concerns about nephrogenic systemic fibrosis (NSF), The European Society of Urogenital Radiology warns against the use of GBCA, including gadofosveset, in children less than 1 year old (40). **Therefore, a significant portion of the children in our study will have immature renal function with an unknown, but likely very low risk of developing NSF.**

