7.2 Study Design Part I: diagnostic efficacy of Feraheme vs. Ablavar

For Part I of our study, the legal guardian(s) of all consecutive pediatric patients with suspected or known CHD referred for cardiovascular MRI will be given the option of having their child undergoing an Ablavar®-enhanced MRI or a Feraheme®-enhanced MRI, after the potential benefits and risks of both agents are clearly explained and their questions addressed. The risks and benefits of using each of these agents will be verbally discussed with the patients' legal guardians and referring cardiologists or cardiac surgeons. A copy of the written IRB-approved informed consent will be provided. Because Feraheme®-based imaging is in use at several pediatric specialty centers, including UCLA whereby Feraheme is used more frequently than GBCA-based imaging for children in our study age-group, in the current state of professional equipoise, we judge it appropriate to allow parents to participate in the choice of agent (see Section 11.1.1 for detailed justification). Those choosing to undergo an Ablavar®-enhanced MRI will be considered the "control" group while those choosing to undergo a Feraheme®-enhanced MRI will be considered enrolled in the "test" group. We plan to recruit 40 patients for test group and 40 patients for the control group with consideration of approximately 10% missing or unusable image quality. To avoid performing a study with larger-than-necessary enrollment, the Investigators will request an interim analysis at 50% enrollment for both groups. If statistical analyses, either as part of interim analyses requested by the Investigators, or after full enrollment, shows statistically significant primary endpoint comparison, we will close Part I enrollment and begin Part II enrollment using the superior agent identified in Part I. If statistical significance is not reached for the primary endpoint during interim analyses, the patient enrollment for both test and control groups will continue until full enrollment, at which time another final statistical analyses will be performed with $p < 0.025$ considered statistically significant. If statistical significance is not reached at full enrollment, we will seek advice from the DMC regarding Part II of the study, including contrast agent to be used.

See Section 11.1.1 for justification for involving the patient's parents in patient group assignment.

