11.1.1 Justification for Parents Participation in Patient Group Assignment

We plan to allow parents to participate in the decision about treatment assignment in Part I of this open-label, evaluator-blinded study. Feraheme-based imaging is in use at several pediatric specialty centers, including UCLA whereby Feraheme is used more frequently than GBCA-based imaging for children in our study age-group. In the current state of professional equipoise, we judge it appropriate to allow parents to participate in the choice of agent. There is no *a priori* reason to expect MRI image quality, ventricular or aortic wall definition, or the risks of anaphylaxis or other important AEs to be influenced by parental preferences; thus the generalizability of our scientific conclusions will not be diminished by allowing parents to influence the treatment assignment for their children. Recruitment of children in clinical studies is a challenging process. Based on our clinical investigative experience in the particular patient population at UCLA, many parents and/or legal guardians are more willing to participate in a study without randomization of treatment than one that required randomization of the child's treatment. We expect this route of recruitment will facilitate recruitment and successful completion of the study. In scenarios where the patient's legal guardians defer and ask the managing clinician to make 'the best choice', the decision will be based on the apparent needs of the trial at the time and the patient will be assigned the group that is under-enrolled with reference to the target enrollment. If our patient group assignment method results in a severely distorted imbalance (e.g. nearly all parents elect either Feraheme or Ablavar), the DMC will be convened and asked to advise on a corrective measure, which may include changing the patient group allocation method.

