18.4 Primary Efficacy Endpoints

18.4.1 Part I – Difference in the composite image quality score between Feraheme and Ablavar

The primary efficacy endpoint for Part I is the composite image quality score, which is defined as the sum of the subject image quality scores assigned to seven important anatomical structures for pediatric CHD patients: the aortic root, the PA, the coronary arteries, the outflow tracts, the valves, the ventricles, and the atria. The score will be the average scores from all the image readers. The consensus reading will occur if the difference in the composite score from the same image is 4 or greater. The composite image quality score will be tested for normality using the Shapiro-Wilk and Shapiro-Francia tests. For normally distributed data, comparison will be made between the composite image quality scores for Feraheme and Ablavar using a parametric two-sided t-test with an appropriate transformation if needed. If statistical transformation of the image quality score is not possible, a non-parametric Wilcoxon-rank-sum test can be considered. The null hypothesis is that there is no difference in the composite subjective image quality scores between Feraheme and Ablavar. This comparison will be a two-sided test at the overall 0.05 level of significance. Summary statistics of mean, standard deviation and their 95% confidence intervals of each contrast agent and the difference will be used for statistical description. There will be a formal interim analysis and a primary analysis for image quality score. The primary analysis of image quality scores will be performed when 80 CHD subjects are enrolled and the images are scored by the image readers. Scores for subjective image quality, sharpness and CNR measurements will remain blinded from the Investigators and only the study statistician will be able to pair the contrast assignment and the score.

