[Interim Analyses]: To avoid performing a study with larger-than-necessary enrollment for Part I of our study, a formal interim analysis for the composite imaging score will be performed at approximately 20 CHD subjects for each of the contrast group (50% of the target number for the primary analysis). Alpha-spending for the interim analyses and the primary analysis will be 0.025 and 0.025 (both two-sided), respectively. The overall alpha for the composite image quality score will be preserved at the two-sided 0.05 significance level. The interim analysis of the composite image quality score will be conducted by an independent statistician under the charter of the DMC.

The interim effect of Feraheme compared to the Ablavar of ventilator-gated MUSIC-MRI based on the average composite score from two image readers will be tested with a two group t-test with an appropriate transformation if needed. Non-parametric Wilcoxon rank sum test will be considered if the data are not normally distributed based on the Shapiro-Wilk and Shapiro-Francia tests and transformation is not feasible.

18.4.2 Part II – Difference in the composite image quality score between ventilator-gated and self-gated MUSIC-MRI

The primary efficacy endpoint for Part II is the composite image quality score defined in 18.4.1. Data will be tested for normality using the Shapiro-Wilk and Shapiro-Francia tests. The composite subjective image quality score will be compared between ventilator-gated MUSIC-MRI and the self-gated MUSIC-MRI using a paired t-test with appropriate transformation if needed. If the data are not normally distributed and transformation is not possible, a Wilcoxon-sign-rank test will be considered. The null hypothesis is that the mean difference in the image quality scores of the self-gated images is smaller than or equal to the mean from ventilator-gated images with the non-inferiority margin of -1.75 (self-ventilator ≤ -1.75). The alternative hypothesis is that the mean difference in image quality score of self-gated images from the ventilator-gated images is greater than the non-inferiority margin of -1.75 (self-ventilator > -1.75) (see the detail of choosing the margin in section 18.7.2.).

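### Part I lets guardians choose the contrast agent but compares scores without adjustment, so an age difference between the groups could bias the result that selects the Part II agent

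*Combined protocol and SAP*

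**What the plan says.** **Allocation.** Under section 7.2, guardians "will be given the option of having their child undergoing an Ablavar®-enhanced MRI or a Feraheme®-enhanced MRI", and they decide "after the potential benefits and risks of both agents are clearly explained and their questions addressed". Section 11.1.1 sends families who defer to whichever group is behind its target. It defends the method on the ground that parental preference should not affect image quality or risk: "thus the generalizability of our scientific conclusions will not be diminished by allowing parents to influence the treatment assignment for their children".

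**Analysis.** For the final look, section 18.4.1 states that "comparison will be made between the composite image quality scores for Feraheme and Ablavar using a parametric two-sided t-test". The interim effect "will be tested with a two group t-test with an appropriate transformation if needed". Both have a Wilcoxon rank-sum fallback, neither has a covariate or stratification, and each look is tested at two-sided 0.025.

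**Consequence.** Under section 7.2, significance at either look closes Part I and the superior agent is carried into Part II. Otherwise, section 7.3 asks the DMC to weigh three factors, two of which are numerical superiority in Part I and the secondary endpoints.

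**Use of age.** Date of birth is recorded (12.1). Sections 18.2 and 18.6 look at results descriptively in three age bands: up to 1 month, 1 month to 2 years, and over 2 years.

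**The concern.** The argument in 11.1.1 is that preference does not act on the image. Confounding does not need that. It needs only something that influences both which agent is chosen and how well the scan scores, and 11.1.1 does not consider a shared cause.

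The protocol points, indirectly, to age on both sides.

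- **Age and choice.** The synopsis raises "concerns of nephrogenic systemic fibrosis (NSF) associated with GBCA injection in young children" below 2 years. Section 4.4 reports that a European radiology society "warns against the use of GBCA, including gadofosveset, in children less than 1 year old". If such points reach families when risks are explained, guardians of the youngest could lean away from Ablavar.
- **Age and score.** In 18.3, small size is one of the listed reasons for grade 1 in all seven structures. Section 4.2 says that resolution needs are more stringent in small children.

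If younger children went mainly to Feraheme and scored lower, a real Feraheme advantage would be understated, or Ablavar would look better when the agents are equal. The opposite pattern would favour Feraheme. In either case the unadjusted result decides which agent is used in Part II, and if Part I is not significant, two of the DMC's three factors rest on the same kind of comparison.

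**Working it through.** **1. The plan's own figures.** Inputs from 18.7.1: difference 1.75, SD 2.10, two-sided 0.025, 20 per group (interim) and 36 per group (final). That 36 is per group follows from 36/(1 − 0.10) = 40. The noncentrality is 1.75 / (2.10 × √(2/n)).

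- n = 20: 1.75 / 0.664 = 2.64 on 38 df, power 62.0% (stated 62%).
- n = 36: 1.75 / 0.495 = 3.54 on 70 df, power 89.1% (stated 90%; the normal approximation gives 90.2%).

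Both figures reproduce.

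**2. Assumed bias.** Bias = score gap between younger and older children × difference in the share of younger children between groups. The documents give neither term. I assume a gap of 1 to 2 points and a difference in share of 20 to 40 percentage points: 1 × 0.2 = 0.2; 1 × 0.4 = 2 × 0.2 = 0.4; 2 × 0.4 = 0.8.

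**3. Effect on the unadjusted t-test.** Same formula, with the bias as the apparent difference when the agents are equal, and 1.75 minus the bias when it runs against the better agent. The either-look column is simulated (20, then 36 per group).

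| Bias | Null rejection, interim | Null rejection, final | Null rejection, either look | Power, interim | Power, final |
|---|---|---|---|---|---|
| 0 | 2.5% | 2.5% | 4.2% | 62% | 89% |
| 0.2 | 3.1% | 3.7% | 5.6% | 51% | 80% |
| 0.4 | 5.1% | 7.5% | 9.8% | 39% | 67% |
| 0.8 | 14% | 26% | 30% | 20% | 36% |

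A second parameterisation agrees: bias = age–score correlation × standardised age difference × SD. 0.3 × 0.2 × 2.10 = 0.13 points gives 4.7% over both looks; 0.3 × 0.5 × 2.10 = 0.32 gives 7.8%; 0.5 × 0.8 × 2.10 = 0.84 gives 33%. Small imbalances matter little.

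**4. What adjustment recovers.** Simulation of the 0.8-point case, 36 per group, within-group SD 2.10, with the drop in score and the imbalance both placed at 1 year or both at 2 years. Entries are null rejection / power for 1.75.

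| Age form | Step at 1 year | Step at 2 years |
|---|---|---|
| None | 26% / 36% | 26% / 36% |
| Linear age | about 5% / 74% | about 4.6% / 78% |
| Section 18.2 bands | about 6% / 72% | 2–3% / 89–90% |
| Under-1-year indicator plus age | 2.6% / 89% | about 4.5% / 77–78% |

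Each form removes most of the bias. The best one is simply the one whose cut-point matches the assumed step. With the step at 2 years, the under-1-year indicator plus age leaves about 0.22 to 0.25 points of bias and does no better than linear age.

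**5. Price when age does not affect score.**

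- Balanced ages, one indicator plus age: 88% final, 60% interim.
- A 40-point imbalance, indicator alone: variance factor 1/(1 − 0.4²) = 1.19, power 83% and 54%. With age added (simulated), 82% and 51%.
- Restoring 89% with the indicator alone would need 36 × 1.19 = 43 evaluable per group, more than the 40 enrolled.
- If age explains 10% of score variance and the standardised age difference is 0.5, linear adjustment gives 90.5% and 64.1%, a gain. At a difference of 0.8 it gives 87.6% and 59.9%.

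**The case against.** The case against is substantial.

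- **The links are thin.** Small size appears only under grade 1, and a Feraheme pilot mean of 25.62 out of 28 (18.7.1) implies that grade 1 is uncommon with that agent. Coils are matched to patient size (12.2.1). Section 4.4 calls the fibrosis risk likely very low and reports no cases in very young children. Nothing available shows that guardians receive age-specific advice.
- **The size is assumed.** A 2-point gap exceeds the pilot SD of 1.82. At the low end, rejection over both looks is 5.6%, barely above the nominal 5%.
- **There are safeguards.** Readers are blinded (11.2), demographics are summarised by group, and efficacy is examined by age band. The DMC is convened "If our patient group assignment method results in a severely distorted imbalance".
- **The stakes are limited.** The study is labelled exploratory, and Part II compares two sequences within each child, so this does not bias that comparison.

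Most of this stands as a limit on size and certainty. It does not remove the gap. Blinding prevents reader bias, not differences between groups. The age bands are descriptive and do not enter the test. The DMC trigger's example concerns how many families choose each agent, so 40 per group with very different ages would not clearly set it off. An adjustment chosen after the scores are seen would carry less weight than one fixed beforehand.

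**Conclusion.** The point holds as a design weakness that should be fixed: a self-selected comparison is tested without adjustment at both looks, and its result picks the Part II agent. The figures above rest on assumed gaps and imbalances, with SD 2.10 and two-sided 0.025, and are illustrations, not estimates for this trial.

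A reader might infer more than the documents support:

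- **That Part I is biased, or biased towards Feraheme.** Neither the presence nor the direction of bias can be established; if the youngest cluster in the Feraheme group and score lower, it runs against Feraheme.
- **That an under-1-year term is required and the 18.2 bands will not do.** The protocol cites both 1 and 2 years, and the ranking of the age forms reverses with the cut-point assumed.
- **That adjustment costs almost nothing.** That is true for modest imbalance only.

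**What to change.** In 18.4.1, before the interim analysis and at the same 0.025 level at both looks:

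1. Make the primary analysis a linear model of composite score on agent, adjusted for age at MRI from date of birth. Fix one form that does not depend on a single cut-point, for example age in years plus indicators at 1 and 2 years. Linear age or the 18.2 bands are acceptable simpler choices.
2. Check normality on the model residuals and name one age-adjusted fallback, for example the same model on ranked scores.
3. Keep the unadjusted t-test or Wilcoxon test as a sensitivity analysis.
4. Show age at MRI by agent in the 18.2 table.
5. Replace the reassurance in 11.1.1 with a statement that measured and unmeasured confounding is possible.

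**Cost.** No new data are needed, and guardian choice and enrolment are unchanged. If age is irrelevant to score, power falls by about 1 to 2 points with balanced ages, and to roughly 82% final and 51% interim with a 40-point imbalance. Those figures are for one indicator plus age; a second indicator costs slightly more. The stated 90% and 62% should therefore be called approximate. The model estimates one average effect across ages and leaves unmeasured confounding, such as disease complexity, in place.

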PLANNED INTERIM ANALYSES	
Part I
 
After 50% enrollment is achieved in both the test and control groups, the Investigators will convene the DMC and request an interim analysis. The Investigators will not be blinded to the treatment assignment or to the images, but only to the image quality scores, which will be provided by independent experienced readers. If statistical significance is achieved for the primary efficacy endpoint in the interim analyses, the Investigators will close enrollment for Part I and will begin enrollment for Part II. If statistical significance is not achieved during the interim analyses, we will continue recruiting patients into the two groups (Feraheme® and Ablavar®) and the final statistical analyses will require a 0.025 level of confidence to claim statistical significance.
 
Part II
 
There will be no interim analyses in Part II of our study.
 
Safety Evaluations
 
Adverse events (AEs) will reviewed and monitored by the DMC on a quarterly basis. SAEs will be reported within 48 hours and the DMC will be convened within one week to evaluate the protocol.

STATISTICS	
PRIMARY EFFICACY ENDPOINTS:
 
Part I: Diagnostic efficacy study in 80 children (age newborn-6 years old) to compare Feraheme®-enhanced and Ablavar®-enhanced MRI
 
Control Group= Ablavar® + MUSIC-MRI Test Group= Feraheme® + MUSIC-MRI

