18.7 Sample Size and Power Estimate for the Primary Efficacy Endpoints

18.7.1 Part I – Difference in the composite image quality score between Feraheme and Ablavar

Sample size and power estimates are based on data from an internal pilot analysis. Based on the average composite image quality scores of two independent readers, the mean image quality score was 25.62 with a standard deviation of 1.82 for the Feraheme-enhanced, ventilator-gated MUSIC-MRI group. The difference in the image quality scores between two readers was a mean of -1.96 with a standard deviation of 2.72. We expect the agreement between two independent readings will improve with consensus reading in cases with largely different image quality scores (4 or more absolute difference in the score).

Based on the above preliminary analyses, for the interim analysis, a sample size of 20 in each contrast agent group will achieve a power of 62% to detect a difference of 1.75 (7% reduction) in the composite image quality scores between the Ablavar group and the Feraheme group with an estimated standard deviation of 2.10 in each group and a significance level of 2.5%.

In the primary analysis, a sample size of 36 subjects will achieve a power of 90% to detect a difference of 1.75 (7% reduction) in composite image quality scores between the Ablavar group and the Feraheme group with an estimated standard deviation of 2.10 in each arm and a significance level of 2.5%. Taking into consideration missing data due to unusable image quality or incomplete studies, we plan to enroll 40 CHD subjects in each group (N=80).

18.7.2 Part II – Difference in the composite image quality score between ventilator-gated and self-gated MUSIC-MRI

The quality of self-gated images are expected to be of at least equal quality to ventilator-gated images with a larger standard deviation due to variation in the methods of respiratory motion gating. We choose the non-inferior margin (87) to ensure that the upper bound of the 95% confidence interval (CI) for the difference between ventilator-gated and self-gated (ventilator – self-gated) is less than 1.75. We expect the mean of the composite image quality score for ventilator-gated images to be approximately 25.62, which is the expected upper limit of the self-gated image quality

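### Part I reports its difference with an unqualified 95% interval and a raw mean, although each look is tested at two-sided 0.025 and Part I may close at the interim

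*Combined protocol and SAP*

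**What the plan says.** Section 18.4.1 sets the Part I primary comparison as a t-test of the composite score: "This comparison will be a two-sided test at the overall 0.05 level of significance". It then lists "Summary statistics of mean, standard deviation and their 95% confidence intervals of each contrast agent and the difference" as the statistics that will serve for description.

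The interim paragraph of the same section splits the error: "Alpha-spending for the interim analyses and the primary analysis will be 0.025 and 0.025 (both two-sided), respectively". The interim is placed at "approximately 20 CHD subjects for each of the contrast group (50% of the target number for the primary analysis").

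The Synopsis (Planned Interim Analyses) gives the consequence: "If statistical significance is achieved for the primary efficacy endpoint in the interim analyses, the Investigators will close enrollment for Part I". Otherwise recruitment continues and "the final statistical analyses will require a 0.025 level of confidence to claim statistical significance". Section 7.2 repeats both rules.

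Section 18.7.1 gives the planning figures: "a sample size of 20 in each contrast agent group will achieve a power of 62% to detect a difference of 1.75 (7% reduction") with SD 2.10, and 90% power with 36 per group at the end. Enrolment is 40 per group to allow for missing or unusable images.

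No section gives a look-specific confidence level, a repeated or stage-wise interval, or an estimate that allows for early stopping.

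**The concern.** A 95% interval corresponds to a test at 0.05. Part I is judged at 0.025, so the interval and the test can point different ways on the same data. The Synopsis makes this easier to misread, because it describes the Part I comparison first at 0.05 and then at 0.025.

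Separately, a trial that stops because the interim difference was large enough to cross a threshold will, on average, overstate that difference if the raw mean is reported. The size of the difference between the two agents is the main quantitative result of Part I, and the plan itself gives a better-than-even chance of ending at the interim if its design effect is true.

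**Working it through.** **Inputs.** From Section 18.7.1: difference 1.75, SD 2.10, 20 per group at the interim, 36 usable and 40 enrolled per group at the end. From Section 18.4.1: two-sided 0.025 per look, 95% interval. Assumptions made here: an unadjusted interval (the plan names no construction), looks at 20 and 40 per group, a repeat at 18 and 36 to reflect the roughly 10% unusable images in Section 7.2, and true differences of 0 and 1.0 to show the range.

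**The plan's own figures.** Two-sample t-test power at two-sided 0.025 (noncentral t) is 62.0% with 20 per group and 89.1% with 36. These agree with the stated 62% and, to within a point, the stated 90%.

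**Where interval and test disagree.** The standard error is SE = 2.10 × √(2/n). The 95% half-width is t(0.975; 2n−2) × SE, and the test at 0.025 needs a difference of at least t(0.9875; 2n−2) × SE.

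- n = 40: SE = 0.470; 1.991 × 0.470 = 0.93; 2.285 × 0.470 = 1.07.
- n = 36: SE = 0.495; 1.994 × 0.495 = 0.99; 2.291 × 0.495 = 1.13.
- n = 20: SE = 0.664; 2.024 × 0.664 = 1.34; 2.334 × 0.664 = 1.55.

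So at the end, an observed difference (in absolute value) of 0.93 to 1.07 with 40 per group, or 0.99 to 1.13 with 36, gives an interval that excludes zero beside a test that has failed. The reverse cannot happen. Nor can it happen in a trial stopped at the interim: a p-value below 0.025 always comes with a 95% interval that excludes zero.

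**Two-look simulation.** Each look uses a t-test at 0.025, Part I stops if the first is significant, and the interval is the unadjusted 95% one at the look where the trial ends.

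| True difference | Looks (per group) | Stops at interim | Disagreement at final look (share of all trials) | Mean estimate if stopped | Mean estimate, all trials | Coverage of 95% interval |
|---|---|---|---|---|---|---|
| 0 | 20, 40 | 2.5% | 2.2% | – | 0 | 93.5% |
| 1.0 | 20, 40 | 22% | 10% | 1.87 | 1.09 | 94.7% |
| 1.75 | 20, 40 | 62% | 3% | 2.14 | 1.87 | 95.1% |
| 1.75 | 18, 36 | 57% | 4% | 2.22 | 1.88 | 95.1% |

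**Inflation at 1.75.** 2.14/1.75 = 1.22 (+22%); with 18 per group, 2.22/1.75 = 1.27 (+27%). Trials that continue average 1.43, so over all trials the mean is 0.62 × 2.14 + 0.38 × 1.43 = 1.87, and 1.87/1.75 = 1.07 (+7%).

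**Type I error.** Under no difference, the chance of rejecting at either look is 4.3% (bivariate normal with correlation √0.5). The unadjusted 95% interval excludes zero in about 6.4% of such trials.

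**A 97.5% interval instead.** It excludes zero exactly when the t-test rejects. Its overall coverage under the stopping rule is 95.7% to 97.5% for true differences from 0 to 1.75. The half-width is 1.07 instead of 0.93 at 40 per group, and 1.55 instead of 1.34 at 20.

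**The case against.** The strongest reply is that the intervals are offered for description only. Significance, closing Part I and starting Part II all rest on the test, so no rule in the plan is broken by a 95% interval. The 95% level also matches the overall two-sided 0.05, the study calls itself exploratory, and the plan does not actually say that the interval is unadjusted. Overall coverage falls by at most about 1.5 points, and the bias over all trials is small at the design effect. The inflated estimate feeds no later calculation: the Part II margin and sample size come from pilot figures and expected means, not from the Part I result.

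All of that stands, and it rules out the stronger readings that a reader might infer. The documents do not support a claim that type I error is inflated, since it is below 0.05. They do not support a claim that the interval is badly wrong overall, or that a Part I stopped at the interim would carry an interval at odds with its test. The near-doubling at a true difference of 1.0 (1.87 against 1.0) rests on an assumed effect and on a stop that occurs in only about a fifth of such trials.

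What the reply does not remove is that the plan, followed as written, can print an interval that disagrees with its primary test, and has no corrected estimate for the branch that it rates at 62%. Section 7.3 also asks the DMC to weigh numerical superiority when Part I is not significant. It does not mention the interval, but that is the branch in which the disagreement can occur.

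**Conclusion.** This is a reporting and estimation gap, not a fault in the decision rule, and it is worth closing in the SAP. At the plan's design effect of 1.75 and SD 2.10, interval and test disagree in about 3% of trials (4% with looks at 18 and 36 per group); at an assumed 1.0 it is about 10%. After an interim stop with 20 per group, the raw difference runs about 22% high on average at a true 1.75, or 27% if only 18 scans per group are usable. These are averages over repeated trials; a single stopped trial need not overstate the effect. The figures assume normal scores, equal SDs, equal group sizes and an interval that ignores the interim look, which is the natural reading of an unqualified 95%.

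**What to change.** In Section 18.4.1:

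- State that statistical significance for Part I rests on the two-sided 0.025 test at each look.
- Report the interval for the Part I difference at the level of the test used at that look, that is 97.5%.
- If Part I stops at the interim, report a median-unbiased estimate with a stage-wise-ordering interval beside the raw difference. The wider interval alone does not correct the point estimate.

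The cost is SAP wording and a few lines of code, best settled before the interim data are unblinded. Enrolment and the stopping rule do not change. The interval becomes somewhat wider and conservative in overall coverage. Exact agreement with the test holds only for the untransformed t-test, so if a transformation or the Wilcoxon test is used, the SAP should say which interval goes with it.
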